6.3 Participant numbering, treatment assignment, randomization

6.3.1 Participant numbering

Each participant is identified in the study by a Participant Number (Participant No.), that is assigned when the participant is enrolled for screening and is retained for the participant throughout his/her participation in the trial. The Participant No. consists of the Center Number (Center No.) (as assigned by Novartis/Sponsor to the investigative site) with a sequential participant number suffixed to it, so that each participant's participation is numbered uniquely across the entire database. Upon signing the informed consent form, the participant is assigned to the next sequential Participant No. available.

6.3.2 Treatment assignment, randomization

No randomization will be performed in this study. The assignment of a participant to a particular cohort will be coordinated by the sponsor depending on the current MS treatment in clinical routine: Cohort 1: continued siponimod treatment without interruption for the purpose of a SARS-CoV-2 vaccination (except for a booster vaccination). Cohort 2: interruption of siponimod treatment for the purpose of a SARS-CoV-2 vaccination. Cohort 3: first-line MS treatment other than siponimod or no current treatment.

7 **Informed consent procedures**

Eligible participants may only be included in the study after providing, IRB/IEC-approved informed consent.

Informed consent must be obtained before conducting any study-specific procedures (e.g. all of the procedures described in the protocol). The process of obtaining informed consent must be documented in the participant source documents.

Novartis will provide to investigators in a separate document a proposed informed consent form that complies with the ICH GCP guidelines and regulatory requirements and is considered appropriate for this study. Any changes to the proposed consent form suggested by the investigator must be agreed by Novartis before submission to the IRB/IEC.

A copy of the approved version of all consent forms must be provided to Novartis after IRB/IEC approval.

8 Visit schedule and assessments

The Assessment Schedule (Table 8-1) lists all of the assessments when they are performed. All data obtained from these assessments must be supported in the participant's source documentation.

Participants should be seen for all visits/assessments as outlined in the assessment schedule (Table 8-1) or as close to the designated day/time as possible. Missed or rescheduled visits should not lead to automatic discontinuation. Participants who prematurely discontinue the study for any reason should be scheduled for a visit as soon as possible, at which time all of the assessments listed for the final visit will be performed. At this final visit, the adverse event and concomitant medications should be recorded on the CRF. Unscheduled on-site visits are possible e.g. to repeat sampling in case of lost or unusable samples, in case of suspected safety issues. Additional telephone visits shall be scheduled in case of booster/refresher SARS-CoV-2 vaccinations to document type and date of the booster vaccination. Additionally, 1 month (+/- 1 week) after a potential booster vaccination a booster visit will be scheduled that includes all assessments performed in the regular study visit 3 including the drawing of blood samples. If this booster visit falls within +/- 1 week of the regular visit 3 or later than the telephone contact in month 12, it will not be performed.

8.1 Documentation of IMPs

Both MS DMTs and SARS-CoV-2 vaccinations are considered as IMPs in this study. As part of drug accountability the following documentation of IMP treatment is required to allow a valid analysis of immune responses to vaccinations in combination with MS treatment.

Documentation of MS DMTs

- At screening
 - Documentation of the current prescription and lot number (Ch-B) of the currently applied MS DMT and number of remaining doses in the package. This information may also be obtained via telephone.
- Investigational epoch (Month 1-12 after vaccination)
 - Documentation of all re-newed MS-DMT prescriptions including lot numbers (Ch-B) of the medication packages. For this purpose, patients should bring any new and empty MS DMT packages (including empty blisters) to the next possible study visit for documentation purposes. Ch-B numbers may also be obtained via telephone contacts.

Should patients fail to bring new or empty MS DMT packages and blisters to the study center even after documented reminders it is also allowed to calculate the compliance from the interval of prescriptions. The compliance as judged by the treating physician shall be documented in the eCRF.

Documentation of SARS-CoV-2 vaccinations

- Vaccination at external site
 - A scan/copy of the "Impfpass" document

- Documentation timepoint of vaccination (date and hour)
- Documentation which external site performed vaccination
- **Vaccination within clinic but outside study site**
 - A scan/copy of the “Impfpass” document
 - Documentation timepoint of vaccination (date and hour)
 - Documentation of department and responsible person for vaccination
 - Confirmation that vaccination was performed according to clinical routine
 - Confirmation that temperature log cannot be obtained
- **Vaccination at study site**
 - **Preparation of syringes directly after delivery to study site**
 - Documentation DSL authorization
 - Documentation timepoint syringe preparation (to make sure 6h at room temperature is not exceeded)
 - Documentation temperature log of refrigerator (if used for storage)
 - A scan/copy of the “Impfpass” document
 - Documentation timepoint of vaccination (date and hour)
 - **Preparation of syringes NOT directly after delivery to study site**
 - Documentation DSL authorization
 - Documentation temperature log of refrigerator
 - Documentation timepoint syringe preparation (to make sure 6h at room temperature is not exceeded)
 - A scan/copy of the “Impfpass” document
 - Documentation timepoint of vaccination (date and hour)

8.2 Participant demographics/other baseline characteristics

Anamnesis, participant demographics (year of birth, sex, race) and relevant medical history/current medical conditions including MS disease and current treatment will be documented.

All prescription medications, over-the-counter drugs and significant non-drug therapies prior to the start and during the study must be documented. See the protocol Section 6.2.1 Concomitant Therapy for further details on what information must be recorded on the appropriate page of the eCRF.

8.3 Screening

Re-screening is not permitted.

8.3.1 Eligibility screening

At screening blood sampling and analysis is performed to check for pre-existing SARS-CoV-2 functional antibodies. If detectable levels are present, the patient is not eligible to further participate in the study. Furthermore, SARS-CoV-2 PCR testing will be performed at screening to exclude current COVID-19 infection. In case of a positive test result, the patient is sent to quarantine and is not eligible to further participate in the study.

8.3.2 Information to be collected on screening failures

Participants who sign an informed consent form and subsequently found to be ineligible will be considered a screen failure. The reason for screen failure should be entered on the applicable Case Report Form. The demographic information, informed consent, and Inclusion/Exclusion pages must also be completed for screen failure participants. No other data will be entered into the clinical database for participants who are screen failures, unless the participant experienced a serious adverse event during the screening phase (see SAE section for reporting details).

Table 8-1 Assessment schedule

Period	Screening	Vaccination [#]		Investigational					COVID-19 follow-up call	
Visit	Screen	Vaccination 1 [#]	Vaccination 2 [#]	1	2	3	booster vaccination ^Q	booster visit ^Q	Call (end of study)	
Day/Week/Month	Day -30 to -3	Day 1*	Week 3/4*	Week +1 (day 8 +/- 2)	Month +1 (day 28-35)	Month +6 (week 25-27)	any time	Month +1 (+/- 1 week) after booster vaccination	Month +12 (week 50-54)	
Obtain informed consent	X									
Inclusion/exclusion criteria	X									
Demography, Relevant medical and MS history	X									
Physical exam including vital signs, height weight	F			S	S	F		F		
SARS-CoV-2 PCR test**	X									
Urine pregnancy test***	X						X		X	
Blood sampling	X			X	X	X			X	
MS relapse	X****	X	X	X	X	X	X	X		
Status MS- and concomitant medication	X	X	X	X	X	X	X	X		X
Documentation SARS-CoV-2 vaccination		X	X				X			
Telephone contact		X	X				X		X	
AE/SAE	X	X	X	X	X	X	X	X	X	

X = assessment to be recorded in the clinical database or received electronically from a vendor

F = full physical exam, S = short medical exam

[#] modRNA vaccination using the same type of compound in both vaccinations independent of study site at designated vaccination centers as part of clinical routine and depending on federal regulations; vaccination will be performed according to respective EU SmPC. Booster/refresher vaccinations are allowed in this study, if suggested by local regulations and performed as part of clinical routine. ^QIf booster/refresher vaccinations are performed an additional telephone contact is required matching documentation parameters shown above for vaccination 1 and 2.

^QFurthermore, an additional study visit will be performed one month (+/- 1 week) after the booster vaccination matching all assessments of investigational visit 3. If this unscheduled visit falls within +/- 1 week of the regular visit 3 or later than the telephone contact in month 12, it will not be performed. * Number of required vaccinations and interval depends on the SmPC of the respective modRNA vaccination. ** Patients need to be sent into quarantine immediately in case of positive test results. Patients in this study are only allowed to continue the study and receive SARS-CoV-2 vaccination after they received a negative PCR test result. *** Required minimum of sensitivity of the pregnancy test is HCG 25 mIU/mL. **** MS relapses within the last two years should be recorded.

8.4 Efficacy

Pharmacodynamic samples will be collected at the time-points defined in the Assessment Schedule (Table 8-1). Follow instructions outlined in the Laboratory manual regarding sample collection, numbering, processing, and shipment.

8.4.1 Efficacy assessment 1

SARS-CoV-2 vaccination efficacy is defined as seroconversion i.e. detection of SARS-CoV-2 serum functional antibodies one week after completion of the vaccination cycle.

8.4.2 Efficacy assessment 2

Additional efficacy assessments are:

- Longitudinal follow-up of SARS-CoV-2 serum functional antibody levels one week, one month and six months after second dose of vaccine and additionally 1 month after a potential booster vaccination
- Longitudinal follow-up of SARS-CoV-2 specific T-cell levels one week, one month and six months after second dose of vaccine and additionally 1 month after a potential booster vaccination

8.4.3 Appropriateness of efficacy assessments

Efficacy assessments in AMA-VACC are based on the study set up of the phase II clinical trial NCT04380701 (EudraCT: 2020-001038-36) for the SARS-CoV-2 vaccination candidate BNT162b1 (Sahin et al., 2020). This study reports SARS-CoV-2 specific IgG antibodies one week after completion of the vaccination cycle at a stable level comparable to a later time-point. Similar results were also reported for mRNA-1273 by Jackson et al, 2020. The detection of specific antibody levels at one week post completion of the vaccination cycle was therefore chosen as primary endpoint.

Furthermore, BNT162b1 was shown to induce a CD4⁺ and CD8⁺ T-cell response (Sahin et al., 2020). Given the mode of action of siponimod targeting TH17 lymphocytes – a subset of CD4⁺ T-cells - it is of importance to understand the T-cell response to a SARS-CoV-2 vaccination in siponimod treated patients. This T-cell response was measured utilizing ex vivo IFN γ enzyme-linked immunosorbent spot (ELISpot) assays in the clinical development of BNT162b1 (Sahin et al., 2020) and was therefore also chosen to assess efficacy in the underlying trial.

8.5 Safety

Safety assessments are specified below with the assessment schedule detailing when each assessment is to be performed.

For details on AE collection and reporting, refer to AE section.

Assessment	Specification
Physical examination	
A complete physical examination will include the examination of vital signs (blood pressure [SBP and DBP] and pulse), height, weight, general appearance, skin, neck (including thyroid), eyes, ears, nose, throat, lungs, heart, abdomen, back, lymph nodes, extremities, vascular, and neurological. If indicated based on medical history and/or symptoms, rectal, external genitalia, breast, and pelvic exams will be performed.
 
A short physical exam will include the examination of general appearance and vital signs (blood pressure [SBP and DBP] and pulse). A short physical exam will be at all visits starting from visit 3 except where a complete physical examination is required (see above).
 
Information for all physical examinations must be included in the source documentation at the study site. Clinically relevant findings that are present prior to signing informed consent must be recorded on the appropriate CRF that captures medical history. Significant findings made after signing informed consent which meet the definition of an Adverse Event must be recorded as an adverse event.

Special clinical laboratory evaluations

All abnormal lab results must be evaluated for criteria defining an adverse event and reported as such if the criteria are met. For those lab adverse events, repeated evaluations are mandatory until normalization of the result(s) or until the result is no longer considered to be clinically significant.

Test Category	Test Name
SARS-CoV-2 vaccination antibody response	Serum functional SARS-CoV-2 antibodies
SARS-CoV-2 vaccination T-cell response	Ex vivo IFNy enzyme-linked immunosorbent spot (ELISpot)

9 Study discontinuation and completion

9.1 Discontinuation and completion

9.1.1 Study treatment discontinuation and study discontinuation

All medication is part of clinical routine.

Discontinuation of study treatment for a participant occurs when study treatment is stopped earlier than the protocol planned duration and can be initiated by either the participant or the investigator.

The investigator must discontinue study treatment for a given participant if, he/she believes that continuation would negatively impact the participant's well-being.

Study treatment must be discontinued under the following circumstances:

- Participant/guardian decision
- Pregnancy
- Use of prohibited treatment as per recommendations in the prohibited treatment section
- New medical condition not allowing for continuation of study treatment
- Any situation in which study participation might result in a safety risk to the participant
- Adverse events, abnormal laboratory values or abnormal test result that indicate a safety risk to the participant.

Study discontinuation of a participants occurs under the following circumstances:

- Significant non-compliance
- Retroactive failure to fulfil inclusion/exclusion criteria
- Enrolment in any other clinical trial involving an investigational product or enrolment in any other type of medical research judged not to be scientifically or medically compatible with this study

Participants who decide they do not wish to participate in the study further should NOT be considered withdrawn from the study UNLESS they withdraw their consent (see Section 9.1.2 'Withdrawal of Informed Consent' section). **Where possible, they should return for the assessments indicated** in the Assessment Schedule. If they fail to return for these assessments for unknown reasons, every effort (e.g. telephone, e-mail, letter) should be made to contact the participant/pre-designated contact as specified in the lost to follow-up section. This contact should preferably be done according to the study visit schedule.

Patients completing the vaccination cycle but do not come to the center for the blood draw one week later (6-10 days after second vaccination) will be excluded from the study.

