- Dose not changed
 - Dose Reduced/increased
 - Drug interrupted/withdrawn
6. Its outcome (i.e. recovery status or whether it was fatal)

Conditions that were already present at the time of informed consent should be recorded in medical history of the participant.

Adverse events (including lab abnormalities that constitute AEs) should be described using a diagnosis whenever possible, rather than individual underlying signs and symptoms.

Adverse event monitoring should be continued for at least 30 days following the last study visit (Covid-19 follow-up call).

Once an adverse event is detected, it must be followed until its resolution or until it is judged to be permanent (e.g. continuing at the end of the study), and assessment must be made at each visit (or more frequently, if necessary) of any changes in severity, the suspected relationship to the interventions required to treat it, and the outcome.

Information about adverse drug reactions for the investigational drug can be found in the Investigator's Brochure (IB).

Abnormal laboratory values or test results constitute adverse events only if they fulfill at least one of the following criteria:

- they induce clinical signs or symptoms
- they are considered clinically significant
- they require therapy

Clinically significant abnormal laboratory values or test results must be identified through a review of values outside of normal ranges/clinically notable ranges, significant changes from baseline or the previous visit, or values which are considered to be non-typical in participant with the underlying disease.

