12.1 Analysis sets

For all analysis sets, participants will be analyzed according to the study treatment(s) received. The safety analysis set will include all participants that received any study drug.

The efficacy analysis sets at one week, one month and six month and additionally after a potential booster vaccination respectively will include all participants who have a valid determination of functional antibodies to SARS-CoV-2 at that time point plus those who failed to receive their second dose of vaccine for whatever reason. The latter will be counted as non-responders. Patients completing vaccination but fail to provide a blood sample at one week after the second vaccination will be excluded from the study and analysis.

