## **2.2 Analysis sets**

For all analysis sets, participants will be analyzed according to the study treatment(s) received.

The safety analysis set (SAF) will include all participants that received any study drug.

The efficacy analysis set will include all participants who have a valid primary endpoint (i. e. determination of functional antibodies to SARS-CoV-2 at Visit 2 / Week 1) plus those who failed to receive their second dose of vaccine for whatever reason.

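### Removing fully vaccinated patients who miss the Week-1 blood draw contradicts Protocol Section 8 and the SAP, and ends their scheduled AE and COVID-19 follow-up

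*Protocol*

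**What the plan says.** Protocol 9.1.1 states that patients who finish the vaccination cycle but do not attend "for the blood draw one week later (6-10 days after second vaccination) will be excluded from the study". Protocol 12.1 repeats the rule more broadly: patients who complete vaccination but "fail to provide a blood sample at one week after the second vaccination will be excluded from the study and analysis".

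Other places read differently:

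- Protocol Section 8: "Missed or rescheduled visits should not lead to automatic discontinuation".
- Protocol 9.1.1 itself, on patients who no longer wish to take part: they "should NOT be considered withdrawn from the study UNLESS they withdraw their consent", and they are asked to return for assessments where possible.
- Protocol 2.1 and 12.3.3: a missing or invalid antibody result after two doses takes the patient out of the efficacy analyses. Leaving the study is not mentioned.
- SAP Section 4 and rule O05 in SAP 5.4: a missing Week-1 result removes the patient only from the denominator of the seroconversion rate. SAP 2.2 nevertheless still defines the efficacy set by a valid Week-1 result.
- SAP 2.2, matching Protocol 12.1: "The safety analysis set (SAF) will include all participants that received any study drug". No Week-1 sample is required.

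**The concern.** A missing efficacy sample is a reason to leave a patient out of one proportion. It is not an obvious reason to stop observing a patient who has had both doses. Table 8-1 schedules AE/SAE recording at Visit 2, Visit 3, any booster visit and the Month-12 call, and blood sampling at all of these except the call. Removal loses all of them. Safety, including patients who develop COVID-19, is a secondary objective, and antibody and T-cell levels at one and six months are secondary endpoints.

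The removed patient still belongs to the safety set. SAP 2.8.1 reports AEs and COVID-19 as numbers and percentages of that set, with no allowance for observation time. A patient with a few weeks of observation therefore counts in the denominator like one with a full year.

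A site cannot follow both 9.1.1 and Section 8, so the handling of a missed draw may differ between sites. The rule also treats a willing patient who misses one sample more strictly than one who wants to stop but has not withdrawn consent.

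**Working it through.** **The plan's own figures.** The plan gives no figure on this point. The one used below is 22 enrolled per cohort (Protocol 12.6.1), which reproduces as 20 × 1.10 = 22. Dividing instead, 20 / 0.90 = 22.2, rounds up to 23; the difference does not matter here.

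**Safety window if the patient stays in.** The Month-12 call falls at week 50 to 54 after vaccination is complete, and the on-treatment period runs 30 days beyond it (Protocol 12.4.1):

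- 50 × 7 + 30 = 380 days
- 54 × 7 + 30 = 408 days

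**Safety window if the patient is removed.** Without a Month-12 call, SAP 5.2 closes the period 30 days after the last visit:

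- last contact at dose 2 (assumed): 0 + 30 = day 30
- discontinuation visit at day 10 (assumed): 10 + 30 = day 40

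**Loss per removed patient.**

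- smallest: 380 − 40 = 340 days, and 340 / 380 = 89%
- largest: 408 − 30 = 378 days, and 378 / 408 = 93%

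**Loss per cohort.** The number removed is not given. If all of the planned 10% drop-out arose this way, 10% of 22 is 2.2, so I take 1 or 2 patients as an assumption. With the call at week 52 (394 days) and removal at day 40, the loss is 354 / 394 = 90% per patient:

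- 1 removed: 1/22 × 0.90 = 4% of the cohort's post-dose-2 time
- 2 removed: 2/22 × 0.90 = 8%

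**Effect on a crude percentage.** One unseen event is 1/22 = 4.5 points. For expected values, assume a 5% late-event risk in patients who stay and a risk of 5% to 50% in those removed, with none of the latter's late events reaching the database. These risks are illustrative and not from the documents.

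- 1 removed: observed 21 × 0.05 / 22 = 4.8%. True (1 × 0.05 + 21 × 0.05) / 22 = 5.0%, up to (1 × 0.50 + 21 × 0.05) / 22 = 7.0%.
- 2 removed: observed 20 × 0.05 / 22 = 4.5%. True 5.0%, up to (2 × 0.50 + 20 × 0.05) / 22 = 9.1%.

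The first value in each pair shows that some understatement arises even when the missed draw has nothing to do with health, because follow-up is lost while the denominator stays at 22. It is then only about 0.2 to 0.5 points.

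**The case against.** The strongest reply is that the rule does far less harm than it seems to. Most of its parts stand.

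- *Safety follow-up does not simply stop.* Section 8 says: "Participants who prematurely discontinue the study for any reason should be scheduled for a visit as soon as possible", with final-visit assessments done and AEs recorded. Protocol 10.1.1 adds: "Once an adverse event is detected, it must be followed until its resolution or until it is judged to be permanent". Protocol 10.1.3 requires SAE reporting until 30 days after the last visit, and of suspected related SAEs after trial completion. A reader might infer that all safety follow-up ends; the documents do not support that. Only the scheduled later contacts are lost.
- *Nobody says that missed draws reflect illness.* It is tempting to read the rule as removing the patients who felt worst after dose 2, which would bias safety results downwards. No passage gives reasons for missed draws. The summary of Amendment 1 offers a logistical one: visits are possible only Monday to Wednesday, so a second dose on a Thursday or Friday leaves a single possible day in the 6-10 day window. A reaction in the first ten days would also fall inside the retained window and could still be counted.
- *The patient is not dropped from the safety set.* The exclusion from analysis in Protocol 12.1 closes the paragraph on efficacy sets. SAP 5.4 excludes patients from the safety set only for lack of consent or of any study treatment.
- *The relapse rate is protected.* SAP 2.7.1 reports it with patient-years, so short observation shortens its denominator too.
- *Cohort 2.* One might infer that the end of the siponimod break goes unobserved. The label text cited in Protocol 1.1 runs to 4 weeks after vaccination, and the SAP window closes at about day 30 to 40, after that mark. No scheduled contact remains in that stretch after the final visit, but the period is not outside AE capture.
- *Care continues.* Treatment is clinical routine and goes on after the study (Protocol 9.2), so these patients are not left without care.

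None of this removes the contradiction between the removal rule and Section 8, or restores the later visits and the Month-12 call.

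**Conclusion.** The point holds as an internal contradiction with a limited practical cost. Protocol 9.1.1 and 12.1 cannot be reconciled with Section 8, and they defeat the purpose of SAP Section 4 and rule O05: the SAP keeps later data that the protocol's rule would prevent from being collected.

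Each removed patient loses about 340 to 378 days of planned safety observation, together with the Month-1 and Month-6 immune data. If 1 or 2 of 22 are removed, that is 4 to 8% of the cohort's post-dose-2 time. AE and COVID-19 percentages may be understated: by a fraction of a point if removal is unrelated to risk, and by several points only under strong assumptions about those removed.

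This rests on three assumptions: the number removed, the timing of the last contact, and late events in removed patients mostly not being reported. The documents do not settle any of them. They also do not show that the rule was ever applied. The SAP revision made after final data review, to keep patients with non-missing secondary data, may suggest that such patients existed, but a missing Week-1 antibody result can also come from an invalid sample.

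**What to change.** - In Protocol 9.1.1 and 12.1, replace exclusion from the study (and analysis) with: *not counted in the Week-1 seroconversion proportion, but remains in the study for all later scheduled visits and the Month-12 call*.
- In SAP 2.2, align the efficacy-set definition with SAP Section 4 and rule O05, so that a valid Week-1 result is needed for the seroconversion rate and not for membership of the set.
- Report by cohort how many patients missed the Week-1 draw, the reasons, and how long they were followed afterwards. SAP 2.3.1 already plans frequency tables of reasons for missed visits.

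Safety-set membership needs no change.

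The cost is two protocol sentences and one SAP sentence. The visits are already scheduled and no procedure is added. The small downside is that a few patients will contribute later data without a Week-1 value. If follow-up is already over, as the SAP's document history suggests, the protocol edit can no longer recover data; the SAP alignment and the by-cohort report still can be done.
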